9.1 Primary Efficacy Analysis

Analysis of primary endpoint (post-operative pain medication at 2- and 24-hours post-surgery) will be performed in accordance with section 9.

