4.2 Endpoints

Primary endpoint:

Requirement of pain medication (if patient experiences a pain intensity of NRS \geq 3) during the first 2 and 24 hours after surgery.

For evaluation of primary endpoint post-operative pain levels need to be evaluated by NRS at 0 min (admission to PACU), 15 min, 30 min, 45 min, 60 min, 75 min, 90 min, 105 min, 2 hours and 24 hours.

Secondary endpoints:

Maximum post-operative pain levels (NRS) within 2- and 24-hours post-surgery.

Post-operative nausea and vomiting (PONV) at 2- and 24-hours post-surgery.

Requirement of antiemetic medication in presence of post-operative nausea and vomiting (PONV) during the first 2 and 24 hours after surgery.

Post-operative comfort at 2- and 24-hours post-surgery.

Post-operative anxiety at 2- and 24-hours post-surgery.

Post-operative mental orientation grade after extubation, at admission to PACU and at 2- and 24-hours post-surgery.

Anesthesia wakeup time (time from end of surgery until extubation).

5 Study Methods

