- (6) Intraop. analgesic drugs Sum of sufentanil dose, sum of fentanyl dose, sum of piritramide dose, sum of metamizole dose, sum of paracetamol dose, sum of COX2-inhibitor (cyclooxygenase 2) dose. Cumulative dosage of non-opioids as percentage of maximum daily dose (maximum daily doses for conversion: metamizole=4000mg, paracetamol=4000mg, ibuprofen=2400mg, diclofenac=150mg).
- (7) **Intraop. analgesic Co-medication** Sum of clonidine dose.
- (8) Postop. analgesic drugs - Sum of opioid dose represented as morphine piritramide=0.7, tilidine=0.2, equivalents (factors for conversion: tramadol=0.1, oxycodone=2.0). Sum of metamizole dose, sum of paracetamol dose, sum of ibuprofen dose, sum of diclofenac dose, sum of COX2-inhibitor (cyclooxygenase 2) dose. Cumulative dosage of non-opioids as percentage of maximum daily dose (maximum daily doses for conversion: metamizole=4000mg, paracetamol=4000mg, ibuprofen=2400mg, diclofenac=150mg).
- (9) **Postop. analgesic Co-medication** Sum of clonidine dose.
- (10) **PONV** (post-operative nausea and vomiting) Items are 'true' or 'false', depending on patient reporting nausea or vomiting within the specified time interval.
- (11) Wengritzky PONV impact scale score (ranging from 0–6), a score of ≥ 5 defines clinically important PONV.⁵
- (12) Intraop. antiemetic medication Sum of granisetron dose, sum of ondansetron dose, sum of dexamethasone dose, sum of droperidol dose.

⁴ Apfel CC, Heidrich FM, Jukar-Rao S, et al. Evidence-based analysis of risk factors for postoperative nausea and vomiting †. Br J Anaesth 2012;109(5):742-53.

⁵ Myles PS, Wengritzky R. Simplified postoperative nausea and vomiting impact scale for audit and post-discharge review. Br J Anaesth. 2012 Mar;108(3):423-9.

- (13) Postop. antiemetic medication Antiemetics Milligram Equivalents
 (ondansetron = 4, dexamethasone = 4, droperidol = 1.25, metoclopramide = 20, dimenhydrinate = 50).⁶
- (14) **Comfort** Scale items are measured ranging from 0 to 10 for which 0 = no comfort and 10 = highest comfort.
- (15) Orientation grade Items are 'full', 'mostly', 'partly' and 'not'. Patients will be asked for their name, location and day of week (3 correct answers = full, 2 correct answers = mostly, 1 correct answer = partly, no correct answer = not).
- (16) Anesthesia wakeup time Time from end of surgery until extubation.
- (17) Adverse events all adverse events during study visits will be documented.

6 Sample Size

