On basis of a 1:1 randomization ratio, we calculated that a planned sample of 368 patients would provide the trial with approximately 80% power to detect a difference in postoperative pain therapy on the basis of an effect size of 0.3 at a two-sided alpha level of 0.05. With 5 participating study centers, approximately 70-80 patients need to be included per center.

The sample size calculation is based on a previously published meta-analysis by Rosendahl et al.⁷ Sample size calculation for a power of 80% was done using G*Power software (University Dusseldorf, Dusseldorf, Germany, http://www.psychologie.hhu.de/arbeitsgruppen/allgemeine-psychologie-undarbeitspsychologie/gpower.html).

⁶ Apfel CC, Korttila K, Abdalla M, et al. A Factorial Trial of Six Interventions for the Prevention of Postoperative Nausea and Vomiting. N Engl J Med 2004; 350(24): 2441-51.

⁷ Rosendahl J, Koranyi S, Jacob D, Zech N, Hansen E. Efficacy of therapeutic suggestions under general anesthesia: A systematic review and meta-analysis of randomized controlled trials. BMC Anesthesiol 2016;16(1).

 Caseley-Rondi et al. 1994; d = 0.459
 Korunka et al. 1992; d = 0.405
 Rosenberg et al. 1992; d = 0.384
 Williams et al. 1994; d = 0.323
 Mastropietro et al. 1998; d = 0.315
 Furlong-Read et al. 1993, d = 0.256
 Nilsson et al. 1993; d = 0.244

7 General Considerations

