8.2 Demographic and Baseline Variables

The following variables are considered to be demographic and baseline:

- Medical condition (diseases, medication). Type of surgery.
- Age, sex.
- Pre-operative NRS, HGSHS-5, STAI-S, and Apfel score.
- Duration of surgery.
- Intra-operative analgesic drug dose (opioids and non-opioids).
- Intra-operative analgesic co-medication.
- Intra-operative antiemetic medication.

Demographic and baseline values will be grouped by treatment groups. If applicable, subgroups may be used in accordance with section 7.3. Differences between groups will be investigated as follows: Student's t-test for normally distributed continuous variables, Mann-Whitney U test for not-normally distributed continuous variables, and Pearson's chi-squared test for categorical variables. Tests will be performed two-sided. A p-value of less than 0.05 will be considered to be statistically significant. Demographic and baseline values with p-value will be presented as a table.

9 Efficacy Analyses

For statistical analyses of outcome variables, values will be grouped by treatment groups. If applicable, subgroups may be used in accordance with section 7.3. All continuous, normally distributed variables will be summarized using the following descriptive statistics: n (non-missing sample size), mean, standard deviation (SD). All continuous, not-normally distributed variables will be summarized using the following descriptive statistics: n (non-missing sample size), median, interquartile range (IQR). The point estimates and 95% CI (based on the non-missing sample size) of observed levels and absolute difference of percentage points with 95% CU as well will be reported for categorical measures.

Differences between groups will be investigated as follows: Student's t-test for normally distributed continuous variables, Mann-Whitney U test for not-normally distributed continuous variables, and Pearson's chi-squared test for categorical variables. Tests will be performed two-sided. A p-value of less than 0.05 will be considered to be statistically significant.

Effect sizes for outcome variables will be described by Cohen's d with 95% confidence interval. For dichotomous outcome variables, differences between groups will be expressed as number needed to treat (NNT).

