9.3 Exploratory Efficacy Analyses

Further analysis of exploratory analyses will be performed in accordance with section 9.

10 Safety Analyses

All adverse events which are directly connected to study procedures will be documented and reported by appropriate statistical methods in accordance with section 9.

Due to the non-invasiveness of the study procedure, no severe adverse events are expected to occur.

11 Figures

The following figures will be considered for presentation in final publication(s):

- Post-operative pain levels (NRS) at 2- and 24-hours post-surgery.
- Post-operative pain levels (NRS) over course of time: pre-operative, at 0 min (at admission to PACU), 15 min, 30 min, 45 min, 60 min, 75 min, 90 min, 105 min, 2 hours and 24 hours.
- Usage of pain medication (opioids as morphine equivalents, non-opioids as percentage of maximum daily dose) at 2 and 24 hours after admission to PACU.
- Post-operative nausea and vomiting (PONV) at 2- and 24-hours postsurgery.
- Requirement/Dosage of antiemetic medication in presence of post-operative nausea and vomiting (PONV) during the first 2 and 24 hours after surgery.
- Post-operative comfort at 2- and 24-hours post-surgery.
- Post-operative orientation grade after extubation, and at 2- and 24- hours post-surgery.

Figure types will be chosen by the trial steering committee and statistician. Measures of central tendency will be presented as mean (normally distributed continuous variables) and median (not-normally distributed continuous variables). Error bars will be presented as SD for normally distributed continuous variables and as IQR for not-normally distributed continuous variables. Bootstrapping technique with resampling may be considered for presentation of non-parametric values with mean and 95% confidence interval, where applicable.

12 Reporting Conventions

P-values ≥0.001 will be reported to 3 decimal places; p-values less than 0.001 will be reported as '<0.001'. The mean, standard deviation, and any other statistics other than quantiles, will be reported to one decimal place greater than the original data. Quantiles, such as median, or minimum and maximum will use the same number of decimal places as the original data. Estimated parameters,

not on the same scale as raw observations (e.g. regression coefficients) will be reported to 3 significant figures.

13 Technical Details

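### The primary endpoint is tested in two unranked windows, each at p<0.05 with no decision rule, so the false-positive rate for the primary claim can reach 9.75% instead of 5%

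*SAP*

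**What the plan says.** Section 4.2 defines the primary endpoint as the need for pain medication "during the first 2 and 24 hours after surgery". It names two windows and ranks neither. Section 9.1 consists of one sentence: "Analysis of primary endpoint (post-operative pain medication at 2- and 24-hours post-surgery) will be performed in accordance with section 9".

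Section 9 is the general efficacy section. It assigns a t-test, Mann-Whitney or chi-squared test according to the type of variable, and adds: "Tests will be performed two-sided" and "A p-value of less than 0.05 will be considered to be statistically significant". The SAP gives no order of testing, no division of alpha, and no statement of whether one or both windows must be significant. Section 7.5 rules out interim analyses, so no alpha is spent there.

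Section 6 bases the 368 patients on "an effect size of 0.3 at a two-sided alpha level of 0.05", with about 80% power. Section 7.1 places the final analysis at 400 patients.

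The measure of pain medication is not fixed either. Note 8 of section 5.4 lists an opioid sum in morphine equivalents, sums for single drugs, and "Cumulative dosage of non-opioids as percentage of maximum daily dose". Among the figures to be considered, section 11 lists "Usage of pain medication (opioids as morphine equivalents, non-opioids as percentage of maximum daily dose) at 2 and 24 hours after admission to PACU". None of these is named as the primary measure.

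**The concern.** A primary endpoint read in two windows gives two p-values. Without a rule that combines them, the plan does not define a positive trial. If only the 2-hour or only the 24-hour result is significant, a reader of the SAP cannot tell whether the primary question was answered yes. If either result is enough, the trial has two chances of a false positive, and the two-sided 0.05 of section 6 no longer describes the primary claim. A choice made after unmasking could follow the data.

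**Working it through.** **Inputs.** Two windows (4.2, 9.1); 0.05 two-sided per test (9); d = 0.3, 80% power, 1:1 allocation, N = 368 (6); N = 400 at final analysis (7.1). The SAP gives no correlation between the windows, so the correlations below are assumptions.

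**Step 1: reproduce 368.** For a comparison of two means, n per arm = 2(1.960 + 0.842)²/0.3² = 174.4, so 175 per arm and 350 in total; the exact t-test gives 176 per arm, 352 in total. For a Mann-Whitney test with normal data (relative efficiency 3/π = 0.955), 184 per arm is needed, 368 in total. The effective n is 184 × 0.955 = 175.7, the noncentrality is 0.3 × √(175.7/2) = 2.81, and the power is 80.1%. The SAP does not name the test behind 368, and 350 × 1.05 = 367.5 would also round to it. On either route, 368 is the size for one comparison at the full 0.05.

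**Step 2: error rate if either window suffices.** With no effect in either window, the rate is 1 − P(|Z₁| < 1.96 and |Z₂| < 1.96), where Z₁ and Z₂ are bivariate normal with correlation ρ. With ρ = 0 it is 1 − 0.95² = 9.75%. By Šidák's inequality this is the maximum for two such two-sided tests.

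| Assumed ρ | Rate |
|---|---|
| 0 | 9.75% |
| 0.3 | 9.5% |
| 0.5 | 9.1% |
| 0.7 | 8.3% |
| 0.8 | 7.8% |
| 0.9 | 7.0% |
| 1 | 5.0% |

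The rate reaches 9% only if ρ is about 0.53 or lower.

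**Step 3: conditional case of four tests.** Suppose opioid and non-opioid use were each tested in both windows and any one result sufficed. Under independence the rate is 1 − 0.95⁴ = 18.5%. A simulation with 2,000,000 draws per setting took a between-window correlation of 0.3 to 0.9 and a between-drug correlation of 0 to 0.5, with the product of the two for cross pairs. It gave 12.6% (0.9 and 0.5) to 18.1% (0.3 and 0).

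**Step 4: effect of possible rules** (Mann-Whitney, d = 0.3).

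- *Fixed sequence.* If the first null hypothesis is true, any false claim requires a false rejection there, which has probability at most 0.05. If it is false, only the second test can err, again at most 0.05. The overall rate is at most 5%. The first test keeps 80.1% power with 368 patients.
- *Equal split at 0.025.* The overall rate is at most 5% (1 − 0.975² = 4.94% if independent). Power per test is 71.2% with 368 and 75.2% with 400. Restoring 80% would take 446 patients.
- *Both windows must succeed.* The rate is at most 5%. If both windows have 80% power and are not negatively correlated, joint power lies between 0.80 × 0.80 = 64% (independent) and 80% (perfectly correlated).

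**The case against.** The strongest objection is that the SAP states no success criterion at all, so the either-window reading is inferred from silence. The two windows could be meant as co-primary, both having to succeed, which would hold the error at or below 5%. It is fair that the inflation is conditional. But the SAP does not state the co-primary rule, and section 6 makes no allowance for the power it would cost. A SAP's section on the primary analysis is the place to choose.

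Three stronger readings are tempting and are not supported:

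- A reader might take about 9% as a floor. For two windows 9.75% is the ceiling. The first 2 hours lie inside the first 24, so positive correlation is to be expected and the rate may be well under 9%.
- A reader might count four primary tests, or six if a yes/no requirement is added. That count comes from a list of recorded variables in section 5.4 and a list of optional figures in section 11. Neither is a test plan. What stands is that the SAP does not exclude such tests, because it names no single measure.
- A reader might add the secondary endpoints, each also judged at 0.05. They are analysed separately under section 9.2 and do not bear on the primary claim. A combined rate that treats them as independent would also ignore that the same scales recur at 2 and 24 hours.

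**Conclusion.** The concern holds, limited to the two windows. The SAP tests its primary endpoint twice at 0.05 with no rule for combining the results, although its sample size allows for one test at 0.05. If significance in either window counts, the false-positive rate for the primary claim is above 5% unless the two tests are perfectly correlated, and it is at most 9.75%. For assumed correlations of 0.9 to 0.3 it is about 7.0% to 9.5%. The range of about 12.6% to 18.5% applies only if opioid and non-opioid use are each tested in both windows and any one result suffices, which the SAP neither states nor rules out. All these figures rest on assumed correlations and on normally distributed test statistics.

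**What to change.** In section 9.1, before unmasking, name one primary pain-medication measure and state that the two windows are tested in a fixed sequence: the first at two-sided 0.05, and the second at 0.05 only if the first is significant. The sponsor chooses the order, since the SAP gives no reason to prefer either. State that the other pain-medication measures are reported with estimates and 95% confidence intervals and are not confirmatory.

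The cost is a few sentences and no extra patients. The first test keeps its full 0.05 and the planned power. The drawback is that the second window cannot be claimed if the first fails, however small its p-value. If that is unacceptable, an equal split at 0.025 or a rule that both windows must succeed would also protect the 5% level, at the cost in power shown in step 4.

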9.2 Secondary Efficacy Analyses

Analyses of secondary endpoints will be performed in accordance with section 9.

9.3 Exploratory Efficacy Analyses

Further analysis of exploratory analyses will be performed in accordance with section 9.

10 Safety Analyses

All adverse events which are directly connected to study procedures will be documented and reported by appropriate statistical methods in accordance with section 9.

Due to the non-invasiveness of the study procedure, no severe adverse events are expected to occur.

11 Figures

The following figures will be considered for presentation in final publication(s):

- Post-operative pain levels (NRS) at 2- and 24-hours post-surgery.
- Post-operative pain levels (NRS) over course of time: pre-operative, at 0 min (at admission to PACU), 15 min, 30 min, 45 min, 60 min, 75 min, 90 min, 105 min, 2 hours and 24 hours.
- Usage of pain medication (opioids as morphine equivalents, non-opioids as percentage of maximum daily dose) at 2 and 24 hours after admission to PACU.
- Post-operative nausea and vomiting (PONV) at 2- and 24-hours postsurgery.
- Requirement/Dosage of antiemetic medication in presence of post-operative nausea and vomiting (PONV) during the first 2 and 24 hours after surgery.
- Post-operative comfort at 2- and 24-hours post-surgery.
- Post-operative orientation grade after extubation, and at 2- and 24- hours post-surgery.

Figure types will be chosen by the trial steering committee and statistician. Measures of central tendency will be presented as mean (normally distributed continuous variables) and median (not-normally distributed continuous variables). Error bars will be presented as SD for normally distributed continuous variables and as IQR for not-normally distributed continuous variables. Bootstrapping technique with resampling may be considered for presentation of non-parametric values with mean and 95% confidence interval, where applicable.

12 Reporting Conventions

P-values ≥0.001 will be reported to 3 decimal places; p-values less than 0.001 will be reported as '<0.001'. The mean, standard deviation, and any other statistics other than quantiles, will be reported to one decimal place greater than the original data. Quantiles, such as median, or minimum and maximum will use the same number of decimal places as the original data. Estimated parameters,

not on the same scale as raw observations (e.g. regression coefficients) will be reported to 3 significant figures.

13 Technical Details

Statistical analyses will be performed using the following computer software. The used version number at the time of writing will be reported.

- The R Project for Statistical Computing (The R Foundation for Statistical Computing, Vienna, Austria).
- SPSS Statistics (IBM Corp., Armonk, New York, NY, USA).
- GraphPad Prism (GraphPad Software Inc., San Diego, CA, USA).

Any outputs will have

- The date and time included
- The name of the code file that produced the analysis
- The author
- A log capturing the version of the software and any external add-on code used.

At the start of any code file there will be a set of comments that give

- the author
- the date and time of writing
- references to inputs and outputs
- reference to any parent code file that runs the child code file

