5.2 Inclusion-Exclusion Criteria and General Study Population

Inclusion criteria:

Patients who have neurosurgery or abdominal-gynecological surgery: Duration of the surgery should be between 1 to 3 hours and the patient must obtain volatile anesthesia. Moreover, the patient has to be aged between 18 and 70 years and must have a risk of post-operative nausea and vomiting (PONV), measured via the "Apfel-Score", of \geq 2.

Exclusion criteria:

- Massive impairment measured with ASA-Score > 3
- Post-operative requirement of ventilation or requirement of intensive care treatment
- Patients with an epidural catheter
- Patient refuses to participate

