5.4 Study Variables

	Baseline	End of surgery (post extubation)	Post-surgery every 15 min (from admission on PACU until 1 h, 45 mins)	Post-surgery at 2 h after admission on PACU	Post-surgery at 24 h after admission on PACU
History ¹	х				
Age, Sex	х				
NRS ²	х		х	х	х
HGSHS-5 ³	х				
STAI-S ⁴	х			х	х
Apfel ⁵	х				
Duration of surgery		х			x
Intra-operative analgesic drugs ⁶		x			
Intra-operative analgesic co- medication ⁷		х			x
Post-operative analgesic drugs ⁸				х	x
Post-operative analgesic co- medication ⁹				х	x
PONV ¹⁰			х	х	
Wengritzky ¹¹				х	x
Intra-operative antiemetic medication ¹²		х			
Post-operative antiemetic				х	x

	Baseline	End of surgery (post extubation)	Post-surgery every 15 min (from admission on PACU until 1 h, 45 mins)	Post-surgery at 2 h after admission on PACU	Post-surgery at 24 h after admission on PACU
medication ¹³					
Comfort ¹⁴				х	х
Mental Orientation ¹⁵		х	At admission to PACU	х	х
Anesthesia wakeup time ¹⁶		х			
Adverse Events ¹⁷		х	х	х	х

- (1) **History** Medical condition (diseases, medication). Type of surgery.
- (2) **NRS** (Numeric rating scale) Items are measured ranging from 0 to 10 for which 0 = no pain and 10 = worst pain imaginable.¹
- (3) **HGSHS-5** 5-item version of Harvard Group Scale of Hypnotic Susceptibility (ranging from 0 to 5).²
- (4) **STAI-S** State Trait Anxiety Inventory Scale (ranging from 20 to 80).³

¹ Hawker GA, Mian S, Kendzerska T, French M. Measures of adult pain: Visual Analog Scale for Pain (VAS Pain), Numeric Rating Scale for Pain (NRS Pain), McGill Pain Questionnaire (MPQ), Short-Form McGill Pain Questionnaire (SF-MPQ), Chronic Pain Grade Scale (CPGS), Short Form-36 Bodily Pain Scale (SF-36 BPS), and Measure of Intermittent and Constant Osteoarthritis Pain (ICOAP). Arthritis Care Res (Hoboken) 2011;63 Suppl 11(S11):S240-52.

² Bongartz W. German Norms for the Harvard Group Scale of Hypnotic Susceptibility, Form a. Int J Clin Exp Hypn 1985;33(2):131-9.

³ Marteau TM, Bekker H. The development of a six-item short-form of the state scale of the Spielberger State-Trait Anxiety Inventory (STAI). Br J Clin Psychol 1992;31 (Pt 3):301-6.

- (5) Apfel Apfel score of risk for postoperative nausea and vomiting (ranging from 0 to 5).⁴

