7.2 Analysis Populations

Analysis will be performed 'per protocol'. All subjects who did not substantially deviate from the protocol as to be determined on a per-subject basis at the trial steering committee immediately before data base lock, will be included in the final analysis.

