8.1 Protocol Deviations

Major deviations are defined as follows:

- Deviation from main study procedure (audio suggestion) like discontinuation during surgery of more than 10 minutes, wrong treatment in contrast to randomization.
- Violation of inclusion and exclusion criteria.
- Missing informed consent.
- Malfunction of the audio player.
- Unexpected transfer to ICU.

Patients with major deviations will be excluded in the 'per protocol' analysis (see section 7.2).

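### The SAP gives two conflicting rules on which adverse events are documented, and names no safety population while its only defined set removes unexpected ICU transfers

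*SAP*

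**What the plan says.** **Which events.** Note (17) to the variable table in SAP section 5.4 reads "all adverse events during study visits will be documented". The table row "Adverse Events ¹⁷" schedules this after extubation, every 15 minutes in the PACU, at 2 hours and at 24 hours. Section 10 reads: "All adverse events which are directly connected to study procedures will be documented and reported by appropriate statistical methods in accordance with section 9". It adds that no severe events are anticipated, because the procedure is non-invasive.

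**Which patients.** Section 10 names no population. Section 7.2 defines a single set: "Analysis will be performed 'per protocol"'. Subjects without substantial deviation, as decided by the steering committee just before database lock, "will be included in the final analysis". Section 8.1 lists the major deviations, among them "Unexpected transfer to ICU", malfunction of the player, and treatment other than that allocated. It then says: "Patients with major deviations will be excluded in the 'per protocol' analysis (see section 7.2"). Section 5.2 has a related exclusion criterion: "Post-operative requirement of ventilation or requirement of intensive care treatment".

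**The concern.** There are two problems, and they compound each other.

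The first is which events enter the database. Five centres each fill in a supplied sheet (section 7.6). A centre following note (17) would record everything, while a centre following section 10 would record only what it attributes to the study procedure. Counts would then not be comparable between centres, and events never written down could not be recovered at analysis. A causal judgement would also be applied before the randomised comparison that could inform it.

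The second is which patients are compared. Unexpected ICU transfer, player malfunction and wrong treatment all arise after randomisation. A safety comparison that leaves these patients out is no longer a comparison of everyone exposed to the procedure. An ICU transfer may itself be a safety outcome, but the SAP names it only as a ground for removal.

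**Working it through.** The SAP gives no adverse-event or ICU-transfer rate, so there is no planned figure to reproduce on this point. The check is a comparison of text, followed by an illustration of scale.

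**Step 1: the two documentation rules.**

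| | Section 5.4, note (17) | Section 10 |
|---|---|---|
| Events documented | all, at study visits | only those connected with the study procedure |
| Events reported | not stated | the same restricted group |
| Relatedness filter | none | yes |
| Who judges, by what criteria | not applicable | not stated |

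If section 10 restricted reporting only, the two could be read together as recording everything and reporting a part. It restricts documentation as well, so that reading fails.

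**Step 2: the population.**

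1. Section 10 sends the reader to section 9 for methods. Section 9 groups values by treatment and names no set.
2. Section 7.2 defines one set, per protocol, for the final analysis. There is no intention-to-treat set and no safety set.
3. Section 8.1 makes unexpected ICU transfer a major deviation and excludes major deviations from that set. Violating an eligibility criterion is also a major deviation. Because section 5.2 excludes post-operative intensive care, a second route leads to the same removal.
4. Section 5.3 says no audio file is played to control patients. If so, removals for interrupted audio or player malfunction would be expected to fall mainly on the intervention arm.

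With no other set available, an analyst following the SAP would compare safety between arms without these patients.

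**Step 3: scale.** Inputs are N = 400 (section 7.1) and an assumed ICU-transfer rate *p*. Expected number removed = N × *p*. Chance that at least one is removed = 1 − (1 − *p*)^N, taking patients as independent.

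| Assumed *p* | 400 × *p* | 1 − (1 − *p*)^400 |
|---|---|---|
| 0.5% | 2 | 0.87 |
| 1% | 4 | 0.98 |
| 2% | 8 | >0.999 |
| 5% | 20 | >0.999 |

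These figures cover both arms together and ICU transfer only. They say nothing about a difference between arms, and the point does not depend on them.

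**The case against.** The case for leaving the plan alone has real parts.

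- **Section 10 never says that safety is analysed per protocol.** Correct. That follows only because no other set exists. A reader might infer that ICU transfers vanish from all results, but the text does not support this: section 8 says all data will be listed by site, treatment and subject, so they may remain in listings. What they drop out of is the comparison between arms.
- **No one is named as judge of relatedness.** Also correct. A reader might infer that blinded treating staff would judge it and so hide a difference between arms. The SAP does not say they would; the independent personnel described in section 5.3 could equally do it. Even if blinded staff did, their errors should be similar in both arms, which may lose events or dilute a difference but need not hide one. The missing rule stands as a gap, with no direction of bias shown.
- **The expected risk is low, and harm is partly covered elsewhere.** Section 10 anticipates no severe events, and the SAP does not rank ICU transfer as the most serious foreseeable event. Pain, nausea and vomiting, anxiety and orientation are endpoints without a relatedness filter. This lowers the stakes, but those endpoints are also analysed in the per-protocol set.
- **ICU removal only applies the eligibility rule, and adverse-event procedures often sit in the protocol.** The first part explains the removal, but it still acts after randomisation. The second excuses a lack of detail; it does not excuse two conflicting rules within one document.

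The direct contradiction and the unnamed population survive these objections.

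**Conclusion.** The point holds in two parts. Note (17) and section 10 contradict each other on which adverse events are documented, and section 10 applies a relatedness filter with no rule for using it. Section 10 also names no population, while the only defined set excludes patients with unexpected ICU transfer, player malfunction or wrong treatment. The second part rests on the reading that, with no other set defined, section 7.2 governs the safety comparison too.

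Its size cannot be derived from the SAP. Under an assumed ICU-transfer rate of 0.5% to 5%, about 2 to 20 of 400 patients would leave the comparison.

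A reader might go further and infer that a finding of no harm is built into the plan. The SAP plans no such conclusion, and safety is not among its objectives or endpoints. The supported statement is narrower: any safety comparison made under this plan could depend on which events a centre chose to record and on which patients were removed. This should be corrected, but given the low anticipated risk it does not threaten the trial's main purpose.

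**What to change.** 1. Reconcile note (17) and section 10 so that both say all adverse events are documented at the scheduled visits and reported by arm. Record relatedness as a descriptor of each event, not as a condition for recording or reporting it, and state who assesses it.
2. Define a safety set in section 7.2 and name it in section 10: all randomised patients on whom headphones were placed, grouped by what was actually played. The section 8.1 deviations of ICU transfer, player malfunction and wrong treatment should not remove patients from this set.
3. Tabulate unexpected ICU transfers by arm in the safety set. No new method is needed: section 9 already plans percentage-point differences with 95% confidence intervals for categorical measures.

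The cost is a few sentences and a somewhat longer safety table. Note (17) and the section 5.4 schedule already call for collecting the events, so no new assessments are required. The change should reach all centres before data are transferred, because unrecorded events cannot be restored afterwards.
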